### 7.3.4 Expedited AE Reporting Period

- The expedited AE reporting period for this study is the entire study duration for an individual participant (from study enrollment until study completion or discontinuation of the participant from study participation for any reason).
- After the protocol-defined AE reporting period, unless otherwise noted, only suspected, unexpected serious adverse reactions (SUSARs), as defined in Version 2.0 of the EAE Manual, will be reported to DAIDS if the study staff become aware of the events on a passive basis (from publicly available information). See Reference Safety Information table as found in the IB for determination of SUSARs.

## 7.4 Study Monitoring

The Protocol Core Team will monitor the conduct and safety of the study via regular summaries by cohort pooled over treatment arms of accrual, baseline characteristics, study conduct (including premature study discontinuations and premature study treatment discontinuations), any missed doses of study treatment/placebo, any reported interruptions of ART, HIV-1 RNA levels  $\geq 200$  copies/mL (see [section 6.2.4/Confirmation of Virologic Failure](#)), data completeness, specimen collection, and AEs. The core protocol team will review the individual participant-level safety data frequently to assess the relation of all reported AEs to study treatment/placebo.

The DAIDS clinical representative will review and assess EAE reports for potential impact on the study participant safety and protocol conduct as per DAIDS policies, guidance documents, and SOPs, as applicable.

The study will undergo interim review at least annually by an independent ACTG-appointed SMC. The first review is anticipated to be review of the first cohort, regarding dose escalation to the second cohort. The SMC will review information by cohort on accrual, baseline characteristics, conduct of the study (including premature study discontinuations and premature study treatment discontinuations), AEs by treatment arm (including core protocol team assessment of relationship to study treatment), CD4+ T cell counts, virologic failures, and HIV-1 RNA levels/suppression over time by treatment arm, and completeness of follow-up and sample availability. In particular, irAEs will be monitored.

After the last enrolled participant in each cohort receives study treatment and completes follow-up through the week 12 visit and the blinded data become available for review by the core team, safety data including the core team decision on relation of AEs to study treatment will be reviewed by the SMC, unblinded to treatment arm, to determine whether to dose escalate or modify the study. Complementing the SMC reviews, a designated study chair or co-chair may notify the SMC of Grade 4 AEs or deaths, as well as notable Grade 3 AEs among the events that the sites email to the core team per section 8.0. An interim review may also be convened if a concern is identified by the DAIDS clinical representative, the study chairs, or study statisticians in consultation with the team. See also [section 10.4](#) for statistical considerations related to interim monitoring.

Detailed plans for study monitoring will be outlined in a Study Monitoring Plan developed by the Statistical and Data Management Center prior to enrollment of the first participant.

## 8.0 CLINICAL MANAGEMENT ISSUES

The recommendations and toxicity management guidelines within this section should be seen as guidelines, and the treating physician should exercise clinical judgment regarding best clinical management, based on the symptoms and condition of the individual participant.

Criteria for participant management, dose interruption (i.e., withholding doses), and treatment discontinuation will be mandated only for toxicities related to cemiplimab/placebo. Toxicities due to drugs in the antiretroviral regimen should be managed according to standard clinical practice, with the goal of maintaining continuous therapy, if possible. Participants must remain at the clinic for observation for 2 hours following the first infusion of cemiplimab/placebo and 30 minutes following the second infusion (see [section 5.1.2](#) for cemiplimab/placebo administration instructions). All participants who receive at least one infusion, including those participants who have an AE, either related or unrelated, are strongly encouraged to stay on study for the duration of the protocol to collect potential AE data and may continue study procedures unless clinically contraindicated.

The grading system for drug toxicities is located in the Division of AIDS Table for Grading the Severity of Adult and Pediatric Adverse Events, corrected Version 2.1, July 2017, which can be found on the DAIDS RSC Web site: <https://rsc.niaid.nih.gov/clinical-research-sites/daids-adverse-event-grading-tables>.

The grading system for suspected or confirmed infusion-related reactions, adrenal insufficiency, and pneumonitis is listed in [sections 8.2, 8.3.4](#), and [8.3.5](#), and can also be found in the National Cancer Institute's Table for CTCAE, version 5.0, found on the National Cancer Institute Web site: [https://ctep.cancer.gov/protocolDevelopment/electronic\\_applications/docs/CTCAE\\_v5\\_Quick\\_Reference\\_5x7.pdf](https://ctep.cancer.gov/protocolDevelopment/electronic_applications/docs/CTCAE_v5_Quick_Reference_5x7.pdf)

NOTE A: The core A5370 study team must be notified within 24 hours by email at [[contact]](mailto:[contact]) regarding any toxicities considered to be associated with cemiplimab/placebo that result in the discontinuation of the infusion.

NOTE B: The core team must be notified within 48 hours by email at [[contact]](mailto:[contact]) regarding any Grade 3 or 4 adverse reactions that are related to study treatment.

NOTE C: The core team must be notified within 24 hours by email at [[contact]](mailto:[contact]) regarding any suspected or confirmed irAE of any grade that are considered to be related to study treatment. In such cases, cemiplimab/placebo should be withheld.

NOTE D: Should there be any question about whether an AE is considered an irAE, sites should withhold cemiplimab/placebo and immediately contact one of the protocol chairs (see contact information in [Protocol Team Roster](#) on page 6).

NOTE E: For toxicities that cause DISCONTINUATION of cemiplimab/placebo, future doses of cemiplimab/placebo should not be given to the participant. Whereas, for toxicities that cause WITHHOLDING of cemiplimab/placebo, there is potential for continued/future doses to be given once the toxicity(ies) in question have been further investigated by site investigator and the study core team.

#### Guidelines for Management of Adverse Events of Special Interest (AESI)

All participants who receive treatment/placebo on this study should be closely monitored for any symptoms or signs related to irAEs including: gastrointestinal (colitis), endocrinopathies (hypo- and hyperthyroidism, adrenal insufficiency, hypophysitis, diabetes), symptoms or signs suggestive of pneumonitis, myocarditis, hepatitis, uveitis, dermatitis, or other irAEs. Such participants must be carefully followed, and managed at the first onset of these clinical symptoms. Sites should discuss any potential immune-related symptom with the A5370 core study team. For example, a high index of

suspicion for immune-related colitis should be maintained in participants who present with diarrhea or other abdominal symptoms, and a high index of suspicion for immune-related pneumonitis should be maintained in participants who present with respiratory symptoms.

Documentation of the immunopathologic nature of a suspected irAE by biopsy confirmation should be considered if there is no other clear cause, and/or when symptoms are severe or persistent. Discussion with the A5370 core study team prior to biopsy or institution of steroid therapy is strongly recommended if feasible. Prompt initiation of appropriate therapy should be instituted as outlined in the specific toxicity sections of the protocol ([sections 8.1-8.6](#)). Additional information is in the IB and a copy of the most current version of the IB should be readily available to study and other medical personnel following study participants.

Infusions of cemiplimab/placebo should be held in any participant who develops a suspected irAE regardless of grade. If the suspected irAE is confirmed as an irAE of any grade OR if the suspected irAE cannot be excluded, infusions should be discontinued. If, however, the AE is attributed to another cause, then infusions can be continued.

#### Case Definitions for irAEs

Based on the emerging safety profile of cemiplimab and other antibodies targeting the PD-1/PDL1 axis [53, 54] the following working case definitions are provided to help investigators distinguish irAEs from non-immune AEs. These case definitions pertain to the more commonly reported irAEs associated with PD-1 inhibition [53, 54] and is not exhaustive of all possible irAEs. Clinical presentations of less common irAEs, including neurologic, musculoskeletal, cardiac, renal, and ocular events [55, 56] should be reviewed in participants with concerning presentations.

The case definitions below have not been validated and are intended only as guidance for investigators to help distinguish irAEs from non-immune AEs. Investigators' clinical judgment may include other factors when determining immune-relatedness. The case definitions for irAEs may evolve as clinical experience increases with cemiplimab and other antibodies targeting the PD-1/PD-L1 axis.

- a. Immune-related rash: Skin examination demonstrates a rash that is usually maculopapular, but other presentations may occur, including papulopustular, follicular, or urticarial dermatitis. Consider dermatologic consultation and biopsy for atypical presentations. Exclude other cause such as virally-induced rash or contact dermatitis.
- b. Immune-related diarrhea/colitis: These events are on a continuum, with diarrhea defined as increased stool frequency, and colitis involving abdominal pain and/or radiologic evidence of colonic inflammation [54]. Onset at 4 to 6 weeks is common [53]. A computed tomography (CT) scan usually demonstrates diffuse colitis [57]. Exclude *Clostridium difficile* or other infectious etiologies and exclude laxative misuse.
- c. Immune-related hepatitis: Laboratory findings are notable for elevated ALT and/or AST that is usually asymptomatic. Viral or other drug-induced hepatitis is excluded. Exclude alcohol-related liver toxicity. If clinically appropriate, consider radiologic

imaging to exclude malignant causes.

- d. Immune-related hypothyroidism: Laboratory findings are notable for elevated TSH associated with low serum free T4. If elevated TSH is detected, it is recommended that free T4 level also be tested. Elevated TSH with low free T4 establishes the diagnosis of hypothyroidism. Hypothyroidism may be asymptomatic or associated with symptoms such as fatigue, constipation, cold intolerance, dry skin, weight gain, and/or bradycardia.
- e. Immune-related hyperthyroidism: Hyperthyroidism should be managed with standard antithyroid pharmacotherapy, and consultation with an endocrinologist is recommended.
- f. Immune-related pneumonitis: Pneumonitis, defined as inflammation of the lung parenchyma, may present as shortness of breath, cough, fever, and/or chest pain. Median time from start of anti-PD-1 therapy to onset of pneumonitis is 2.6 months [57], but delayed onset of pneumonitis has been reported. The most common radiologic pattern on chest CT scan has been described as cryptogenic organizing pneumonia, but other radiographic patterns may occur [58]. If performed, biopsy may demonstrate lymphocyte-predominant interstitial pneumonitis with areas of organizing pneumonia [58]. Exclude infectious causes of pneumonitis.

NOTE: For any severe (Grades 3-4) irAE, if symptoms worsen or do not improve on adequate corticosteroids within 48 to 72 hours, consider adding additional immunosuppressive agents (to be selected from agents such as: infliximab, cyclophosphamide, cyclosporine, mycophenolate mofetil). Referral of the participant to a specialized unit for assessment and treatment should be considered.

## 8.1 Toxicity

All AESIs must be reported and the study team notified within 24 hours of identification (see [sections 7.2, 7.3, and 8.0](#)), and include the following:

- Grade 2 or greater infusion-related reactions
- Grade 2 or greater allergic/hypersensitivity reactions
- All immune-related, treatment-related toxicities (irAEs) regardless of grade

### 8.1.1 Grade 1 or 2 Toxicity

Participants who develop a Grade 1 or 2 AE or toxicity that occurs following infusion of cemiplimab/placebo, not specifically discussed below nor a possible irAE, and that is associated with symptoms and thought to be related to cemiplimab/placebo should be discussed with the study team. The site should notify the A5370 core team as soon as possible by email at [[contact]](mailto:[contact]).

Participants who experience a Grade 1 or 2 AE that is judged not to be related to the study drug by the investigator, may continue study treatment at the discretion of the site investigator.

### 8.1.2 Grade 3 Toxicity

Participants who develop a Grade 3 AE that occurs following an infusion of cemiplimab/placebo not specifically discussed below nor a possible irAE, and that is thought to be related to cemiplimab/placebo should be discussed with the study team. The A5370 core study team must be notified within 48 hours by email at [[contact]](mailto:[contact]). The participant should be followed closely and if the AE does not return to Grade ≤2 within 2 weeks, the study team should again be notified within 48 hours by email at [[contact]](mailto:[contact]).

Participants who experience a Grade 3 AE that is judged not to be related to the study drug by the investigator, may continue study participation at the discretion of the site investigator in consultation with the study team.

### 8.1.3 Grade 4 Toxicity

Participants who develop a Grade 4 AE that occurs following an infusion of cemiplimab/placebo not specifically discussed below nor a possible irAE, and that is judged by the site investigator to be study drug-related, should be discussed with the study team. The core team must be notified within 48 hours by email at [[contact]](mailto:[contact]).

All participants experiencing Grade 4 AEs should be followed closely with additional clinical assessments and laboratory testing as clinically indicated in consultation with the study team. If the AE does not return to Grade ≤2 within 2 weeks, the study team should again be notified within 48 hours by email at [[contact]](mailto:[contact]).

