### 7.3.2 Reporting Requirements for this Study

- The SAE Reporting Category, as defined in Version 2.0 of the DAIDS EAE Manual, will be used for this study.
- The study agents for which expedited reporting are required are: cemiplimab (anti-PD-1 mAb) and placebo for cemiplimab.
- In addition to the EAE Reporting Category identified above, other AEs that must be reported in an expedited manner are: All AESIs as noted in [section 7.2](#) felt related to study treatment.

If a particular sign/symptom is not specifically listed in the Division of AIDS Table for Grading the Severity of Adult and Pediatric Adverse Events, corrected Version 2.1, July 2017, refer to the Estimating Severity Grade section for the 'Clinical Adverse Events Not Otherwise Identified in the DAIDS AE Grading Table' grading scale.

NOTE: Possible DILI (or Hy's Law) is defined as any elevated ALT and/or AST of Grade 2 or greater ( $\geq 3 \times \text{ULN}$ ), alkaline phosphatase  $< 2 \times \text{ULN}$ , and an increase in bilirubin  $\geq 2 \times \text{ULN}$  with no other immediately apparent possible causes of AST or ALT elevation and hyperbilirubinemia (such as concomitant use of atazanavir), including, but not limited to, viral hepatitis, pre-existing chronic or acute liver disease, or the administration of other drug(s) known to be hepatotoxic.

AESI: All AESIs, serious and non-serious, must be reported using the same reporting process as for SAE reporting.

Other AEs that must be reported in an expedited manner (i.e., within 3 business days to the sponsor or designee) are as follows.

Pregnancy: Although pregnancy is not considered an AE, it is the responsibility of the investigator to report to the sponsor (or designee), within 3 business days of identification, any pregnancy occurring in a female or female partner of a male participant, during the study or within 26 weeks of the last dose of study drug.

Any complication of pregnancy affecting a female study participant or female partner of a male study participant, and/or fetus, and/or newborn that meets the SAE criteria must be reported as an SAE. Outcome for all pregnancies should be reported to the sponsor.

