## 10.5 Data and Safety Monitoring

If at any time within a given dose cohort:

- a) Three or more participants experience a Grade  $\geq 3$  AE related to study treatment ([section 10.2.1.1](#)) (as judged by the core team, blinded to treatment arm); or
- b) Two or more participants experienced an irAE (not including an infusion reaction AE) ([see section 10.4.1B](#)) that is related to study treatment (as judged by the core team, blinded to treatment arm); or
- c) One or more participants experience a Grade 4 clinical AE or death and related to study treatment (as judged by the core team, blinded to treatment arm);

then enrollment into the study and treatment infusions will be temporarily suspended and the SMC, unblinded to treatment assignment, will be asked to review all safety data; review the relation to study treatment of the event(s) thought by the blinded core team to be a primary safety outcome; and recommend how the study should proceed with respect to resuming enrollment, continuing study treatment and dose escalation.

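### One related Grade 4 clinical event or death pauses the trial, yet core-team notice may take up to 48 hours for the residual Grade 4 class and has no stated limit for some related deaths

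*Protocol*

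**What the plan says.** The pause rule is in Protocol 10.5. Its third limb reads "One or more participants experience a Grade 4 clinical AE or death and related to study treatment", with relatedness judged by the blinded core team. When it is met, enrollment and infusions stop and the study monitoring committee (SMC) reviews the safety data. The first limb needs three participants with related Grade 3 or higher events. The second needs two participants with qualifying irAEs.

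The notice clocks are in Protocol 8.0 and 8.1:

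- NOTE A: 24 hours, "regarding any toxicities considered to be associated with cemiplimab/placebo that result in the discontinuation of the infusion".
- NOTE B: 48 hours, "regarding any Grade 3 or 4 adverse reactions that are related to study treatment".
- NOTE C: 24 hours, "regarding any suspected or confirmed irAE of any grade that are considered to be related to study treatment".
- 8.1: 24 hours for adverse events of special interest (AESIs), meaning irAEs of any grade and Grade 2 or higher infusion-related or allergic reactions.
- 8.1.2: 48 hours for a related Grade 3 event in the residual class.
- 8.1.3: "The core team must be notified within 48 hours by email at" the study address, for a Grade 4 event "not specifically discussed below nor a possible irAE, and that is judged by the site investigator to be study drug-related".

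Section 7.4 adds that "a designated study chair or co-chair may notify the SMC of Grade 4 AEs or deaths", and describes these as coming from the events that sites email under section 8.0.

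**The concern.** A pause that one event can trigger works only as fast as the message that starts it. The core team must judge relatedness, and under 6.3.5 the study leadership tells the sites that a pause is in force. Until the core team hears of the event, other participants in the cohort can still be randomized and infused.

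For one class of event, the clocks run opposite to the trigger. A related, life-threatening event that no toxicity section foresaw has the longest limit, while events that cannot pause the trial alone have a shorter one. For some related deaths, section 8.0 gives the core team no clock at all, and the reference in 7.4 leads to notices that do not name death. This is the first study of an anti-PD-1 antibody in otherwise healthy people with HIV, who receive no direct benefit. The unforeseen severe event is therefore the one the pause most needs to catch.

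**Working it through.** **Step 1: clocks against triggers.** This step compares texts; the plan gives no figure to reproduce.

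| Related event | Core-team notice | Number needed to pause (10.5) |
|---|---|---|
| Grade 4 clinical, not a possible irAE, not an AESI, in no toxicity section, not stopping an infusion | up to 48 h (8.0 NOTE B, 8.1.3) | 1 |
| Grade 4 irAE | 24 h (NOTE C, 8.1), though NOTE B's 48 h also covers it as worded | 1 |
| Grade 4 infusion reaction, colitis, liver | 24 h (8.2.4, 8.3.1.4, 8.3.2.4) | 1 if clinical |
| Grade 4 adrenal, pulmonary, cardiac, renal, neurologic, uveitis, skin, platelets, neutrophils | immediately (8.3.4 to 8.6) | 1 if clinical |
| Death from an irAE, another AESI or an infusion-stopping toxicity | 24 h (NOTES A and C, 8.1) | 1 |
| Any other related death | none stated; NOTE B ends at Grade 4 | 1 |
| Grade 3, residual class | 48 h (NOTE B, 8.1.2) | 3 |
| Grade 1 irAE | 24 h (NOTE C, 8.1) | 2, and only for pneumonitis, adrenal insufficiency, myocarditis, diabetes or uveitis (10.4.1 B) |

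The mismatch is confined to the first row and the row for other related deaths.

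**Step 2: size of the delay.** Inputs are 15 participants per cohort with two infusions each, so 30 infusions, and accrual of 3-4 months per cohort (10.1), or about 13-17 weeks. Adding 6 weeks to the second infusion gives 19-23 weeks. Even spacing is an assumption.

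- Rate: 30/(19 × 7) = 0.226 per day, down to 30/(23 × 7) = 0.186 per day.
- Expected infusions in 24 h: 0.19-0.23. In 48 h: 0.37-0.45.
- Chance of at least one, 1 − exp(−rate × days): at 24 h, 1 − exp(−0.186) = 17% to 1 − exp(−0.226) = 20%. At 48 h, 1 − exp(−0.373) = 31% to 1 − exp(−0.451) = 36%.

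The second day therefore adds about 0.2 expected infusions. Leaving out the affected participant's own two infusions (28 instead of 30) gives 16-19% and 29-34%.

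**Step 3: how often it could arise.** Table 10.4.1-1 includes true rates of 0.01 and 0.10 for related Grade 4 or higher clinical events. Among 12 treated, the chance of at least one is 1 − 0.99^12 = 11% and 1 − 0.90^12 = 72%. These are ceilings for the present point, because only some such events fall in the two affected rows.

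**The case against.** The strongest reply is that the 48-hour class is small. The sentence in 8.1.3 excludes possible irAEs and everything covered by a later toxicity section, and nearly all foreseeable Grade 4 events carry 24 hours or immediate contact. NOTE D also asks sites to contact a protocol chair immediately if irAE status is in doubt. This stands. A reader might infer that every related Grade 4 event is slow to reach the core team, or that notice may come after 48 hours. Neither is so: the limit is a maximum, and it governs a remainder.

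It can also be said that the 24-hour irAE notice has its own purpose, since an irAE of any grade ends that participant's dosing, so clocks need not rank by pause threshold. That is fair. The two clocks do not contradict each other; the point is that the residual limit does not serve the single-event pause.

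Three further inferences are tempting but unsupported:

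- That no related death has a clock. One from an irAE, another AESI or an infusion-stopping toxicity has 24 hours.
- That a death may wait "within 3 business days to the sponsor or designee". In 7.3.2 those words introduce other expedited reports, followed by pregnancy. Deaths are serious adverse events handled under the expedited-reporting manual, which is not at hand, and that route is not stated as core-team notice.
- That the permissive wording in 7.4 defeats SMC review. That sentence complements the scheduled reviews and has no relatedness test, while 10.5 already makes review mandatory once a trigger is met.

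Finally, the delay matters only during dosing. Follow-up runs to week 48, so a late event may leave no infusions in that cohort to prevent, and suspension still needs the core team's judgment after notice.

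**Conclusion.** The point holds in a narrow form. For a related Grade 4 clinical event in the residual class, the trial's only single-event pause can be held back by a notice limit of up to 48 hours. For a related death outside the irAE, AESI and infusion-stopping routes, no timed core-team notice exists, although 7.4 presumes one.

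If such an event occurs during dosing and the full limit is used, the chance that someone else in the cohort is infused before the core team knows is about 31-36%, against 17-20% under a 24-hour limit. These figures rest on evenly spaced infusions over 19-23 weeks and are conditional on a rare event. They do not give the overall risk to the cohort. The gain is small but bears directly on safety. No stated figure in the plan is wrong.

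**What to change.** Reconcile 8.0 NOTE B, 8.1.3 and 7.4 with 10.5(c):

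- Name death in the section 8.0 core-team notice, so that the reference in 7.4 leads to a real requirement.
- Align notice of any event that can alone trigger the 10.5(c) pause with the 24-hour core-team email already used in NOTES A and C. Related Grade 3 events can stay at 48 hours.
- State in NOTE B that NOTE C governs irAEs, so that a Grade 4 irAE does not fall under two limits.

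Making the chair's SMC notice in 7.4 mandatory for 10.5(c) events would be an optional alignment edit.

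These changes concern reporting time only. They leave the pause thresholds and the rules for withholding or stopping treatment as they are. The cost is a few lines of wording, and sites send a rare email up to a day earlier.
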